7.1.1 ANALYSIS OF THE PRIMARY ENDPOINT(S)

The primary analysis will be an interrupted time series comparison of acute stroke treatment rates in the three Flint hospitals. The pre-intervention period will be defined using EMR data prior to the start of the roll out of the community intervention. All patients admitted with a primary diagnosis of ischemic stroke in both the pre-intervention and intervention periods will be included in the primary analysis. Note: process measures evaluating the Stroke Ready campaign (quadrant crossover or music video view IP address) will not be linked to any obtained PHI. Logistic regression will be used to estimate the overall intervention efficacy (indicator variable) in a model predicting receipt of acute stroke treatment (binary variable). If a temporal trend exists in the pre-intervention period, we will adjust for the month since the start of the pre-period as a fixed effect while accounting for clustering at the hospital level. To maximize statistical power, both interventions (hospital-HUM00112536 and all community quadrants-this current protocol) will be parameterized with a single variable. With this approach, statistical power for the primary analysis will be more than adequate. Using hospital administrative and Medicare data, we estimate that at least 480 strokes per year will occur at the 3 Flint hospitals for a total of at least 1,440 strokes in the pre period and 1,800 in the post-period, but to be conservative we are requesting data from 2010 to 2021 about 8000 patients with a stroke. Assuming a doubling in treatment rates (pre-intervention Medicare treatment rate 2.2%),³⁷ we will have over 90% power to detect this difference considering a two-sample binomial difference in proportions. This estimate is consistent with prior simulation work based on ARIMA analyses (effect size of 1.0 (pre-intervention monthly treatment rate = 2.2%, standard deviation = 2.1, predicted post-intervention treatment rate 4.3%, auto-correlation=0.3).³⁸

7.1.2 SECONDARY ANALYSES: REGIONAL COMPARISONS AND QUADRANT-BASED ANALYSES TO ENHANCE CAUSAL INFERENCE

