Secondary analyses will explore the extent that such confounding may influence the primary analysis and enhance the ability to draw causal inferences from the primary analysis. First, we will repeat the primary analysis with a concurrent control group consisting of other large Michigan metropolitan regions (regional control model) where African-Americans make up more than 25% of the population (Detroit, Saginaw, Muskegon, Benton Harbor). This analysis will control for regional effects that may lead to increased treatment rates that occur simultaneously with our intervention in Flint using data from the Michigan State Inpatient Database (SID),³⁹ which collects de-identified data on all acute care hospitalizations in the state of Michigan within a given year. Second, by delivering the intervention sequentially to geographic quadrants within Flint, we will explore whether increases in acute treatment rates parallel the geographic pattern of intervention roll out (geographic model). Specifically, each stroke patient in Flint will be geocoded to one of the four intervention quadrants using EMR data and a geocoding interface. Our primary analysis will then be repeated by modifying the intervention indicator variable to represent whether the intervention was active in the patient's geographic quadrant at the time of intervention.

7.1.3 EXPLORATORY ANALYSES: EFFICACY OF PROGRAM COMPONENTS AND TEMPORAL PATTERNS TO INFORM FUTURE INTERVENTIONS

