To inform future interventions, will also perform a series of hypothesis-generating analyses to inform which elements of the program were most effective and the temporal properties of the program. Due to power concerns, our primary analysis does not consider the difference between the hospital and community effects. Thus, we will first estimate the proportion of the change in the acute stroke treatment rate attributable to the hospital-based intervention vs. the community-based intervention by repeating our geographic model including an indicator variable representing the time period of the hospital intervention as well as a community interaction term. In this way, we will be able to explore whether the Stroke Ready hospital or community based intervention was the most efficacious and whether there was synergy between the interventions. The stepped wedge design is a key innovation to this end. In typical multi-level interventions when all of the elements are rolled out nearly simultaneously, it is impossible to estimate which elements have the highest leverage, however with the stepped wedge design it is possible to gain a greater understanding of which elements are most important. Using simulation analyses, we estimate that there will be 70% power to find a doubling at the community level, 55% power to find a doubling at the hospital level and 21% power to find a doubling through a community-hospital interaction. Because this power is inadequate for a hypothesis-testing evaluation, we have specified this analysis as an exploratory analysis whose purpose is enhance our understanding of the importance of intervention elements and to inform future interventions. Second, we will determine the temporal properties of the Stroke Ready intervention by adding a linear slope term and exploring quadratic terms in our geographic model to estimate the time delay between intervention and changes in treatment rates and whether treatment rates level off or decline as the intervention persists into its latter years. Finally, a strength of our data collection approach is that we will be able to inexpensively assess the sustainability of intervention effect using Michigan SID data years after the intervention is completed without needing to perform additional data collection. Together, such analyses will determine the sustainability of the intervention and inform future interventions.

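### The secondary geographic model (7.1.2) has no hospital-intervention term, so part of a hospital-caused rise in treatment can load on the quadrant coefficient

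*Combined protocol and SAP*

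**What the plan says.** Three consecutive sections define the models.

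- **7.1.1 (primary):** "both interventions (hospital-HUM00112536 and all community quadrants-this current protocol) will be parameterized with a single variable". Calendar time is conditional: "If a temporal trend exists in the pre-intervention period, we will adjust for the month since the start of the pre-period as a fixed effect". Clustering by hospital is to be accounted for.
- **7.1.2 (secondary, geographic model):** "Our primary analysis will then be repeated by modifying the intervention indicator variable to represent whether the intervention was active" in the patient's quadrant. No hospital term is mentioned. The section presents its analyses as a way to probe confounding and strengthen causal inference.
- **7.1.3 (exploratory):** the plan describes "repeating our geographic model including an indicator variable representing the time period of the hospital intervention as well as a community interaction term". The hospital term is therefore an addition at this stage and is not part of the 7.1.2 model. The section gives power of 70% (community), 55% (hospital) and 21% (interaction) and calls this inadequate for hypothesis testing.

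Section 2.2 places the hospital intervention at Hurley Medical Center, one of the three hospitals supplying data. Sections 1.2 and 4.2 give a roll-out of four quadrants in six-month steps.

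**The concern.** The geographic model is the plan's internal check that treatment rose where and when the community campaign was active. Only the community arm is rolled out by quadrant. Section 4.1 also presents staggered delivery as the way to see the community effect apart from the hospital one.

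Quadrant exposure only accumulates over calendar time. If the emergency department intervention raises treatment from some date onward, later months have both higher rates and more exposed quadrants. A model with a quadrant indicator and no hospital term can then show a community-shaped association when the community effect is nil.

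Accounting for clustering by hospital does not prevent this. A hospital main effect absorbs a constant difference between hospitals, not a change within one of them.

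**Working it through.** **1. The plan's own figure.** Inputs from 7.1.1: "a total of at least 1,440 strokes in the pre period and 1,800 in the post-period", and a doubling from 2.2% to 4.4%. Two-sided 5% is assumed, because no alpha is stated.

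- Pooled rate = (1,440 × 0.022 + 1,800 × 0.044) / 3,240 = 0.0342.
- SE under the null = √[0.0342 × 0.9658 × (1/1,440 + 1/1,800)] = 0.00643.
- SE under the alternative = √[0.022 × 0.978/1,440 + 0.044 × 0.956/1,800] = 0.00619.
- Power = Φ[(0.022 − 1.96 × 0.00643) / 0.00619] = Φ(1.52) = 93.6%.

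This agrees with the stated power of over 90%. The 70/55/21% figures cannot be checked, because the simulation inputs are not given.

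**2. Set-up for the geographic model.**

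- From the documents: 480 strokes a year = 40 a month; 1,440/40 = 36 pre-months; 1,800/40 = 45 post-months, or 24 if the study duration in 1.1 is used; base rate 2.2%; six-month steps.
- Assumed: equal quadrants (10 strokes per quadrant-month); one third of strokes at the intervention hospital; hospital start from 12 months before to 6 months after launch; true community OR 1.00; no inflation for clustering.

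Two hospital effects are used. In one, the odds double at that hospital. In the other, that hospital alone takes the overall rate to 4.4%. Its own rate must then be 3 × (0.044 − ⅔ × 0.022) = 8.8%, an OR of (0.088/0.912)/(0.022/0.978) = 4.3.

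**3. One case by hand (both start at launch, 45 post-months, no time term).** Unexposed quadrant-months are 4 × 36 + (0 + 6 + 12 + 18) = 180, of which 36 fall after the start. Exposed quadrant-months are 4 × 45 − 36 = 144, all after the start. At 10 strokes each, that is 1,800 unexposed and 1,440 exposed strokes.

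- *Extreme case:* exposed rate 4.4%; unexposed rate (144 × 2.2 + 36 × 4.4)/180 = 2.64%. OR = (0.044/0.956)/(0.0264/0.9736) = 1.70. SE of log OR = √[1/(1,440 × 0.044 × 0.956) + 1/(1,800 × 0.0264 × 0.9736)] = 0.195. z = 0.529/0.195 = 2.71, so rejection is about 77%.
- *Odds doubled at the hospital:* its rate is 4.3%, so the overall post-start rate is (2 × 2.2 + 4.3)/3 = 2.90%. The unexposed rate is 0.8 × 2.2 + 0.2 × 2.90 = 2.34%. OR = 1.25, SE 0.221, z = 1.00, so rejection is about 17%.

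**4. All start dates, 24 and 45 post-months.** These are logistic fits to expected counts by month, quadrant and hospital. Each cell gives the quadrant OR and the chance of p < 0.05. Adding a hospital main effect alone changes almost nothing, and the ranges cover both forms.

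| Model | Odds double at hospital | Hospital alone doubles overall rate |
|---|---|---|
| No time term | 1.15–1.27; 8–19% | 1.38–1.82; 27–85% |
| Linear month term | 0.92–1.13; 5–6% | 0.82–1.33; 5–12% |
| Hospital-specific term added | 1.00; 5% | 1.00; 5% |

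With the month term, ORs below 1 arise when the hospital intervention starts before launch.

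**5. Quadrant and step terms instead (both start at launch).** If the hospital's share is equal across quadrants, the OR is 1.00. With assumed shares of 60/40/25/10% in roll-out order and 45 post-months, it is 1.12 (hospital OR 2) or 1.20 (hospital OR 4). With the order reversed it is 0.89 or 0.83. Rejection is 5.5% and 6.9%. With 24 post-months the same fits give 1.19 and 1.36, or 0.84 and 0.74 reversed, with rejection 6.1% and 9.7%.

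**The case against.** Several points on the other side stand.

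- **Section 7.1.3 already plans the same model with a hospital-period indicator and an interaction, and gives low power as the reason for keeping it exploratory.** A reader might infer that the plan never separates the two effects; it does. But nothing in 7.1.2 says its coefficient should be read through the 7.1.3 model.
- **Section 7.1.2 does not call the quadrant coefficient a community-only effect.** Its stated purpose is to probe confounding of a primary analysis that targets the combined programme. A reader might infer that the whole hospital effect is credited to the community. The text does not say so, and the fits show only part loading on the quadrant term, with a sign that can reverse.
- **The documents give no dates for the hospital intervention.** Overlap in the same months is an assumption, as are the hospital's share of strokes and how that share varies by quadrant.
- **The largest figures need a hospital OR of about 4.3 and no time term.** Much of the problem is therefore lack of calendar adjustment, and any Flint-wide rise would load in the same way. The part that survives quadrant and step terms is modest, and random ordering of quadrants leaves its direction unsystematic.

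The month term is not a reliable safeguard, however. It enters only if a pre-intervention trend exists. A hospital intervention that starts at or after launch creates no such trend, and the unadjusted bias is largest for those start dates.

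**Conclusion.** The concern holds in a limited form. As written, the 7.1.2 geographic model omits a known co-intervention, and part of a hospital-caused rise can appear in the quadrant coefficient. The distortion is moderate if the odds double at the hospital, and large only in the extreme case. It shrinks and can change sign with a month term, and is modest and of either sign with quadrant and step terms. All sizes depend on the assumed start date, share of strokes and even spread across quadrants.

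The primary analysis is unaffected, because it estimates the two interventions together by design. This is a change worth making to a secondary analysis, not a flaw in the main result.

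**What to change.** In 7.1.2:

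- Add an exposure term equal to 1 for patients at the intervention hospital on or after its start date, plus that hospital's main effect. State the start date.
- Report the quadrant coefficient from this model as the geographic result, next to the unadjusted one.
- State that the unadjusted coefficient is not a community-only effect.

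Keep the interaction in 7.1.3 as exploratory.

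The cost is wording and two model terms. They need the treating hospital and admission date, which the planned hospital data supply (6.2, 8.1), plus the hospital start date. Power for a community doubling (2.2% to 4.4%), with a one-third share and no time terms, falls from about 94% to 85–90% with 45 post-months, or from about 80% to 70–76% with 24. If the month term is in the model, power is already only about 47% or 44%, and the hospital terms cost about one further point.

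The hospital-specific form is cheaper than a period-only indicator of the kind 7.1.3 describes. In the same main-effects fits, the latter leaves 42–76% (45 post-months) or 40–64% (24).

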7.1.4 ANALYSIS OF THE SECONDARY AND TERTIARY ENDPOINT(S)

Changes in the proportion of patients arriving by ambulance over time will be assessed using logistic regression with an indicator variable representing the intervention period. Changes in IV tPA will be evaluated using an interrupted time series comparison of acute stroke treatment rates in the three Flint hospitals.

Changes in the time from ED presentation to acute stroke treatment and door to treatment will be explored using linear regression with a similar indicator variable representing the intervention period. Changes in outcomes measured with the community survey across intervention waves will be assessed with ordinal logistic regression (Likert-based outcomes) or chi-squared tests (binary outcomes) with indicator variables representing the survey wave. Process and satisfactory measures will be summarized with descriptive statistics, as pre-intervention values will be either unmeasurable or unintelligible, formal statistical comparisons will not be performed.

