1 PROTOCOL SUMMARY**1.1 SYNOPSIS**

Title:	Stroke Ready: A Community Based Participatory Trial to Increase Stroke Treatment
Grant Number:	U01MD010579
Study Description:	Stroke Ready is a health behavior theory-based, multi-level intervention, designed to increase acute stroke treatment in Flint, MI. The hospital-level intervention aims to optimize acute stroke hospital care in a safety net ED. Meanwhile, the community intervention seeks to increase acute stroke treatment (by decreasing pre-hospital delay). Stroke Ready also aims to inform future stroke preparedness interventions by exploring the relative importance of hospital optimization and community interventions.
Objectives:	To increase acute stroke treatment rates in Flint, Michigan through a two-pronged approach of hospital and community level interventions. To inform future CPBR acute stroke interventions by exploring both the relative importance of community and hospital interventions.
Endpoints:	
Primary Endpoint:
 
 Acute Stroke Treatment Rates (tPA and endovascular treatment) 
Secondary Endpoints:
 
 Acute Stroke Treatment Rates (tPA) Number of emergency department arrivals by ambulance
Study Population:	Adults in the Flint Community
Description of Study Intervention/Experimental Manipulation:	Stroke Ready is a community based, health theory based, peer-delivered intervention delivered in a stepped wedge design to each of the four Flint community quadrants over the course of 2 years
Study Duration:	24 months
Participant Duration:	Single-session

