Specific Aim 1: To adapt and expand our CBPR-developed, theory-based, Stroke Ready pilot community intervention and implement a hospital-based intervention to optimize acute stroke care in an urban safety-net, hospital.

Specific Aim 2: To increase acute stroke treatment rates in Flint, Michigan through a two-pronged approach of hospital and community level interventions.

Specific Aim 3: To inform future CBPR acute stroke treatment interventions by exploring both the relative importance of community and hospital interventions and the efficacy of the intervention on processes mediating the outcome.

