3 OBJECTIVES AND ENDPOINTS

Table 2: Stroke Ready Program Outcome Measures			
Intervention Goal	Outcome Measure	Data Source	Data collection
Primary Outcome			
Increase acute stroke treatments	Acute stroke treatment rate (IV and EVT)	Flint Hospitals and State Inpatient Database	2010-2021
Secondary Outcomes			
Increase acute stroke treatments	Acute stroke treatment rate (IV only)	Flint Hospitals and State Inpatient Database	2010-2021
Optimize community for acute stroke	ED arrival by ambulance	Flint Hospitals	2010-2021
Tertiary/Exploratory Outcomes			
Optimize ED for acute stroke treatment	Time from hospital arrival to acute stroke treatment	Hurley hospital EMR/GWTG	About 3 years prior to project to 2021
Increase Stroke Preparedness	Time from stroke symptom onset to hospital arrival	Hurley hospital EMR/GWTG	About 3 years prior to project to 2021
Improve self-efficacy, attitude, social norms	Self-efficacy, Attitude, subjective norm	Community Surveys (STYH and FAST)	2015, 2017, 2019, 2021
Increase Stroke Preparedness	Stroke recognition, intent to call 911	Community Surveys (STYH and FAST)	2015, 2017, 2019, 2021
Provide community stroke education	Exposure to local stroke education	Community Surveys (STYH and FAST)	2019, 2021

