4.2 SCIENTIFIC RATIONALE FOR STUDY DESIGN

Flint is naturally divided into 4 quadrants by the cross streets of Saginaw Street and 5th Avenue. The Stroke Ready community intervention will be sequentially delivered to each quadrant, eventually reaching the entire community. Quadrants will be randomly selected and then for 6 months the research team will focus on the selected quadrant of the city (Table 1). During this time the peer workshops will occur, flyers and posters distributed and workbooks made available. At the end of six months, the materials will remain in the quadrant but efforts will shift to the next quadrant. Delivery of the intervention in quadrants will: 1) allow more efficient use of resources; 2) optimize intervention efficacy by increasing the likelihood of repetitive exposure to the intervention and 3) allow for exploratory analyses to determine whether the hospital or community intervention is most important and clarify the efficacy of the overall intervention.

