Tertiary/exploratory outcomes: The tertiary/exploratory outcomes include onset to door time and door to needle time which will be obtained from the hospital EMR and GWTG. Survey data will also be obtained. The community survey, Speak to Your Health, is a biennial, geo-coded survey that has been designed and administered by the Flint community, Genesee County Health Department since 2003.³⁵ We added questions from the Stroke Ready pilot (HUM00098718) (including stroke attitude, self-efficacy, social norms, and written stroke preparedness vignettes) to this community survey (see Appendix B) that was administered in 2015/2017 and will continue in 2019 and possibly 2021. The research team may add stroke education exposure questions to the 2019 and 2021 STYH surveys (see section 29 of IRB application- exposure questions). These additions, along with the original questions, will assess community level change in response to the Stroke Ready program; as well as exposure to local stroke education (See Appendix B). Additionally, these same questions will be added to the Flint Area Study. This is a face to face interview of Flint residents. The survey data will be de-identified. STYH and FASt surveys are ongoing surveys in Flint. The data is de-identified and publically available.

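### The survey outcomes are modelled by wave alone, so change across waves cannot be read as an effect of Stroke Ready, and a change of survey source between waves is not controlled

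*Combined protocol and SAP*

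**What the plan says.** Section 7.1.4 compares survey outcomes across waves using ordinal logistic regression for Likert items and "chi-squared tests (binary outcomes) with indicator variables representing the survey wave" for binary items. Wave is the only predictor named.

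The purpose given is causal. Specific Aim 3 (Section 2.1) includes exploring "the efficacy of the intervention on processes mediating the outcome", and Section 6.2 says the survey items will assess community change in response to the programme.

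On timing, the Section 3 outcome table gives the waves as "2015, 2017, 2019, 2021". The intervention is "delivered in a stepped wedge design to each of the four Flint community quadrants over the course of 2 years" (Section 1.1), and Section 4.2 says "Quadrants will be randomly selected and then for 6 months the research team will focus on the selected quadrant of the city". No launch date or survey field dates are given. Section 8.1 mentions workshop participant forms collected from June 2018 to January 2019.

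On source, the Section 3 table names both Speak to Your Health and the Flint Area Study against all four years. Section 6.2 puts the stroke questions in Speak to Your Health in 2015/2017 and says that survey "will continue in 2019 and possibly 2021". It then says that "these same questions will be added to the Flint Area Study. This is a face to face interview of Flint residents". Speak to Your Health "is a biennial, geo-coded survey that has been designed and administered by the Flint community"; its mode of administration is not stated.

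**The concern.** A wave indicator measures calendar change in the whole city. It becomes a programme effect only if nothing else moved the answers and the respondents had a common exposure status. Neither is secured here. The quadrants cross over one after another, so a wave fielded during roll-out averages residents whose quadrant has been reached with residents whose quadrant has not. There is no comparison area for the surveys. If the mix of surveys differs between waves, a difference between surveys also enters the wave coefficient.

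For treatment rates, Section 7.1.2 recognises confounding of this kind and adds a regional control model and a geographic model. Neither is specified for the surveys. At stake is the reading of the self-reported mediators under Aim 3. Secular or source change could be taken for programme success, and dilution in 2019 could be taken for failure.

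**Working it through.** The plan states no sample size, power or effect size for the survey outcomes, so there is no planned figure to reproduce.

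**1. Where 2019 falls in the roll-out.** Inputs: four quadrants; 6-month steps (Section 4.2), described as about six months in Section 5.3, so 6 and 7 months were tried; workshops running by June 2018 (Section 8.1). The launch month is an assumption, varied from January to June 2018. For calendar month m:

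- started = number of q in 0, 1, 2, 3 with m ≥ launch + q × step
- completed = number of q with m ≥ launch + (q + 1) × step

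| Launch, step | Quadrants started during 2019 | Completed |
|---|---|---|
| Jan 2018, 6 months | 3 (Jan–Jun), 4 (Jul–Dec) | 2, 3 |
| Jan 2018, 7 months | 2 (Jan–Feb), 3 (Mar–Sep), 4 (Oct–Dec) | 1, 2, 3 |
| Mar 2018, 6 months | 2 (Jan–Feb), 3 (Mar–Aug), 4 (Sep–Dec) | 1, 2, 3 |
| Mar 2018, 7 months | 2 (Jan–Apr), 3 (May–Nov), 4 (Dec) | 1, 2, 3 |
| Jun 2018, 6 months | 2 (Jan–May), 3 (Jun–Nov), 4 (Dec) | 1, 2, 3 |
| Jun 2018, 7 months | 2 (Jan–Jul), 3 (Aug–Dec) | 1, 2 |

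In no scenario had none started or all four completed. The latest finish (June 2018 plus 4 × 7 = 28 months) is the end of September 2020. A 2021 wave would therefore follow roll-out, but Section 6.2 makes Speak to Your Health 2021 only possible.

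**2. Dilution.** Assume equal quadrant populations and an effect confined to crossed quadrants. The city-wide contrast is then effect × k/4 with k quadrants crossed. A 10-point effect appears as 10 × 1/4 = 2.5, 10 × 2/4 = 5.0 or 10 × 3/4 = 7.5 points, and as the full 10 points when k = 4. This concerns only quadrant-delivered components; Table 1 (Section 1.2) shows broadcast and internet media in every quadrant from Time 1.

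**3. Non-programme change.** As an illustration, assume a 50% baseline, a two-sided 5% test, no programme effect, and a 5-point shift between two waves from secular or source change. With n respondents per wave and p̄ = 0.525, the chance of a significant result is approximately

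Φ{[0.05 − 1.96 √(2p̄(1 − p̄)/n)] / √[(0.5 × 0.5 + 0.55 × 0.45)/n]}.

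At n = 500 this is Φ[(0.05 − 1.96 × 0.03158)/0.03154] = Φ(−0.38) = 35%. At n = 300 it is 23%, and at n = 1,000 it is 61%. For a 3-point shift the three sizes (300, 500, 1,000) give 11%, 16% and 27%. The survey sizes and shifts are assumptions, not document figures.

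**4. Source.** Set side by side, the Section 3 table has both surveys contributing in all four years. Section 6.2 has Speak to Your Health carrying the questions in 2015/2017, the Flint Area Study receiving them at an unstated future time, and Speak to Your Health uncertain for 2021. On the Section 6.2 reading, a late wave could come partly or wholly from a survey with no documented baseline. No section says how the two surveys are combined.

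**5. Exposure item.** The Section 3 table lists exposure to local stroke education for 2019 and 2021 only, so it has no pre-intervention wave and a before/after comparison is impossible.

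**The case against.** These outcomes are tertiary or exploratory in a study that calls itself quasi-experimental, and they do not touch the primary result. Separate wave indicators keep 2015 and 2017 as two pre-intervention points, and a 2021 wave would come after roll-out, so the mixing is confined to 2019. All of this stands and limits the severity. It does not supply a control for secular change in any wave, nor a source term.

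A quadrant contrast has its own faults. City-wide media cancels out of it, Section 5.3 allows workshops outside the current quadrant, there are only four clusters, and the contrast disappears if all four quadrants had started when the 2019 survey was fielded. This stands too, and it is why the contrast can support the wave comparison but should not become the main result.

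Four stronger readings are tempting and are not supported:

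- A reader might infer that the interview mode changes between waves, or that a 2021 wave would be wholly face to face against a baseline of another mode. Only the Flint Area Study is called face to face. The mode of Speak to Your Health is never stated, and the Section 3 table lists both surveys for every year.
- A reader might infer that the surveys are the only behavioural evidence for Aim 3. Ambulance arrival (secondary) and time from onset to hospital arrival (tertiary) also bear on behaviour.
- A reader might fix the 2019 dilution at 50–75% of the effect. That rests on an assumed June 2018 launch and leaves out December 2019. Counting quadrants started, the scenarios above give 2 to 4 of 4, or 50–100%.
- A reader might take a null 2019 quadrant contrast as failure of the programme. It would speak only to what workshops, mailers and print add to city-wide media.

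**Conclusion.** The point holds in a limited form. The wave-only model in Section 7.1.4 cannot carry the causal reading that Aim 3 and Section 6.2 give it. The 2019 wave very probably mixes quadrants at different stages (2 to 4 started, 1 to 3 completed). This is inferred from the form dates and step length, because launch and field dates are not given, and launches before January 2018 were not examined. Survey source, and possibly mode, may change between waves, and the model would not detect it. The size of any resulting bias cannot be computed from the documents; the figures in steps 2 and 3 show only what is plausible under the stated assumptions. Severity is low, but the change is cheap and worth making.

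**What to change.** In Section 7.1.4:

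- **(a) Source.** Analyse Speak to Your Health and the Flint Area Study separately, or include a survey-source term. Do not compare a Flint Area Study wave with a Speak to Your Health baseline. Reconcile the Section 3 table with Section 6.2 on which survey carried the questions in which year.
- **(b) Wave comparison.** Keep it, but label it descriptive of calendar change.
- **(c) Supporting analysis.** In parallel with the geographic model of Section 7.1.2, fit logistic or ordinal logistic regression with wave, quadrant and an indicator that the respondent's quadrant had crossed over by the interview date, where the geo-code resolves to quadrant. Only Speak to Your Health is described as geo-coded.

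State with (c) that it estimates only the added effect of workshops, mailers and print over city-wide media, with four clusters and possible contamination from out-of-quadrant workshops. For the exposure item, if only one wave is available, crossed-over status within a single step is determined by quadrant. The quadrant terms must then be dropped and the contrast read as descriptive. State the roll-out dates and survey field dates so that the indicator can be defined.

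The cost is revised analysis wording and a quadrant code on data that are planned anyway, assuming the released geo-code is fine enough. The downside is wider intervals and a narrower estimand for (c).
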